3.3 Entomological collections for indoor-resting mosquitoes

We lack preliminary entomological data from the trial area to inform a meaningful sample size calculation but owing to budget limitations and a smaller effect size expected than in the Sud Ubangi trial, it is unlikely that we will be able to power the trial sufficiently to compare abundance between arms. Therefore, our aim is to perform sampling to capture the vector community diversity across the trial area for which we aim to sample from approximately 10 health areas from the BBNet arm arm chosen using stratified random sampling from those included in the trial. Collections will be performed by the team from Kinshasa School of Public Health. Teams will working in pairs (preferably a male/female combination wherever possible). Collectors will be trained to take informed consent and will use mechanical Prokopack aspiratorsto collect from a target of 20 houses per health area per arm per survey round. Collections will take place in early morning (6-10am) and householders will be requested to keep doors and windows closed as much as possible and to leave bednets in place. Following initial approach householders will have 24h to decide whether they wish to take part. Compensation will not be provided for the collections. The information leaflet and consent form are provided in **Appendix D**. A total of approximately 200 houses will be sampled.

4. Study Outcome Variables

4.1 ANC1 malaria prevalence

Women who visit their first ANC and consent to take part in the study will asked to allow their malaria test result to be recorded and to complete a questionnaire (**Appendix E**) which requests basic demographic information, information on stage of pregnancy and number of previous pregnancies, the type(s) and numbers of bednets and their use, and - *if their household received a BBnet* - the hanging status of the barrier under which they sleep by reference to pictures on the questionnaire form. Additional information will be the health area within which their home is located to identify if this is different from that in which the ANC1 is visited. Test results and questionnaires will be anonymous and no personally-identifiable information will be requested. Data will be recorded onto forms and stored securely at the health facility as well as onto mobile phones to allow prompt electronic transfer to the study team. Monitoring of ANCs will take one during a 3-month window at 7-9 months after the distribution.

4.1.1 Secondary epidemiological outcome

Malaria cases and RDT-confirmed malaria in the population will be approximated as cases per capita using population size estimates from the distribution team for each health area. These will be obtained from routine DHIS2 data for each heath area for comparison of trends with those from the ANC1 data.

4.2. Survey of mosquito community

4.2.1 Rationale for entomological surveillance

Owing to the low expected mosquito catches (\approx 0.5/house) in houses receiving new PermaNet 3 bednets and high expected standard deviation of catches (\approx 3x mean) (Sud Ubangi trial data, unpublished data) suitably-powered entomological comparisons of *Anopheles* female abundance to detect an expected reduction of e.g. 30% with BBnets would require more clusters than are present

within the study, or even if clustering is not considered, larger sample sizes than are feasible for this study ($N \approx 2400$ houses). Therefore, the aim of entomological sampling will be characterisation of the local malaria mosquito community (species composition, insecticide resistance and mechanisms) rather than comparative assessment of abundance between arms.

4.2.2 Number of houses surveyed

We aim to obtain a target number of *Anopheles* females of at least 100 per survey round, which based on our experience gives an appropriate sample size for estimation of species composition and molecular marker frequencies. The survey will aim to obtain a representative sample from across the trial area. To give a representative sample, 200 houses will be sampled including each of 7 health zone targeting clusters in the BBNet arm. A survey round will be performed during later periods of the trial.

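### All 200 indoor mosquito-collection houses are placed in the BBnet arm, which does not fit the aim of representing the trial area, the durability sample in both arms, or the target of at least 100 females

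*Protocol*

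**What the plan says.** Protocol section 4.2.2 sets the target as "females of at least 100 per survey round". On coverage it says "The survey will aim to obtain a representative sample from across the trial area", and on the sample itself it says "200 houses will be sampled including each of 7 health zone targeting clusters in the BBNet arm".

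Section 3.3 gives the same total: about ten health areas from the BBnet arm, chosen by stratified random sampling, with 20 houses in each. In the same paragraph, however, it states the 20 houses as a number per health area and per arm.

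Section 4.2.1 supplies the planning figures. It expects about 0.5 mosquitoes per house "in houses receiving new PermaNet 3 bednets", a standard deviation of about three times the mean, and gives as its example the sample needed to "detect an expected reduction of e.g. 30% with BBnets". Without clustering it puts that sample at about 2400 houses, and on that ground it drops any between-arm comparison of abundance.

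Section 4.3 takes nets from 30 houses per arm. These are to be a subset of the collection houses, with no more than three per health area, and are drawn from a second survey round. The lay summary and section 4.2.2 plan only one round.

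**The concern.** Three parts of the plan do not fit together.

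- **Aim and sampling frame.** A survey meant to describe the vector community across the trial area draws its adult mosquitoes from one arm. The protocol's premise is that the barrier kills more resistant mosquitoes, so indoor-resting females in BBnet houses might differ in species mix or marker frequency from those in PermaNet 3 houses. A one-arm sample cannot show whether they do.
- **Durability sample.** If collections take place only in BBnet areas, the collection houses include no PermaNet 3 areas from which to draw the PermaNet 3 durability houses. The net assessment in that arm cannot be carried out as written.
- **Target catch.** The figure of 100 matches the PermaNet 3 catch rate, but the houses are all in the arm where the protocol expects fewer mosquitoes. With a single round, no later collection can make up a shortfall.

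**Working it through.** **Inputs.** From section 4.2.1: mean 0.5 per house with PermaNet 3, SD about 3 x mean, example reduction 30%, about 2400 houses for a comparison. From section 4.2.2: 200 houses, target 100. From section 4.3: 30 durability houses per arm, at most three per area. From section 2.4: 5% type I error and 80% power, with a two-sided test in the Stata output. These are stated for the primary endpoint, and I assume they also apply to the 2400. I read 0.5 as *Anopheles* females; if it covers all mosquitoes, the shortfall is larger.

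**1. The plan's own figure.** The BBnet mean is 0.5 x (1 - 0.30) = 0.35, so the difference is 0.15. With SD = 3 x mean in each arm (1.5 and 1.05):

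n per arm = (1.5² + 1.05²) x (1.96 + 0.842)² / 0.15² ≈ 1170, total 2340.

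This is within 3% of 2400. Other SD choices give 2270 (average SD, two-sided), 2474 (common SD 1.5, one-sided) and 3140 (common SD 1.5, two-sided). The check shows that 0.50 and 0.35 are plausible inputs to the stated figure. It does not fix the SD in BBnet houses.

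**2. Expected catch from 200 houses.** Catch = 200 x 0.5 x (1 - reduction) if all houses are in BBnet areas.

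| Reduction with BBnets | Expected catch, all 200 in BBnet areas |
|---|---|
| 0% | 100 |
| 10% | 90 |
| 20% | 80 |
| 25% | 75 |
| 30% | 70 |
| 40% | 60 |

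Any reduction puts the expectation below 100. At 30%, an expected 100 needs 100 / 0.35 ≈ 286 BBnet houses.

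**3. Chance of reaching 100.** Negative binomial counts summed over 200 independent houses:

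- BBnet houses, mean 0.35, SD 1.05: about 3%.
- BBnet houses, mean 0.35, SD 1.5: about 9%.
- PermaNet 3 houses, mean 0.5, SD 1.5: about 48%.

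Clustering of catches within areas would widen the spread around these expectations.

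**4. Half the houses in each arm.** 100 x 0.5 + 100 x 0.35 = 85 expected. The chance of reaching 100 is about 21% (BBnet SD 1.05) to 23% (SD 1.5).

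**5. Durability arithmetic.** 30 houses at no more than three per area need 30 / 3 = 10 areas in each arm. The present plan has about ten BBnet areas (enough) and no PermaNet 3 areas (0 x 3 = 0). A split of five and five areas would allow only 5 x 3 = 15 per arm.

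**6. Zone coverage.** Appendix G lists both arms in all seven zones. BBnet areas number 8, 2, 2, 3, 2, 3 and 1, and PermaNet 3 areas 10, 4, 10, 6, 4, 6 and 2, for Ruashi, Lubumbashi, Kampemba, Tshamilemba, Kenya, Mumbunda and Kisanga. Ten areas per arm can therefore reach every zone in both arms.

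**The case against.** The catch figures are not a forecast for this survey. The 0.5 is unpublished Sud Ubangi data for new nets, the 30% is offered as an example, and section 3.3 says there are no preliminary entomological data from the trial area. The nets will be many months old at collection, and a BBnet whose barrier is not hung protects like a PermaNet 3 (section 2.5). All of this stands. A reader might infer that the survey will miss its target. The documents support only that the target does not follow from the protocol's own figures once the houses are placed in the BBnet arm.

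A reader might also infer that BBnet-only sampling biases the resistance results. That is not shown. BBnet areas were chosen at random, both arms span the same seven zones, and mosquitoes resting in PermaNet 3 houses have also been exposed to deltamethrin and PBO. Phenotypic resistance is tested on larvae from public spaces with no arm restriction (section 4.5). What remains is a risk for the adult species, infection and marker data, which a one-arm sample cannot examine. Nor is a between-arm abundance comparison lost, since the protocol expressly does not plan one.

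The loss of precision is small. For a proportion of 0.5, the simple 95% half-width, 1.96 x √(0.25/n), is 9.8 points at n = 100, 10.6 at 85 and 11.7 at 70. That limits the weight of the shortfall but leaves the contradictions in place.

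Finally, the questionnaire survey in section 3.2 covers both arms equally and could supply durability houses. Section 4.3 does not use it, however; it names the collection houses.

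**Conclusion.** The point holds as an internal inconsistency with a modest consequence. The strongest part needs no assumption: sections 3.3 and 4.2.2 confine collections to the BBnet arm, while section 4.3 and the per-arm wording in section 3.3 presuppose collections in both arms. The stated aim of representing the trial area also sits badly with leaving out the arm that holds two thirds of the clusters, with no reason given.

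The second part is conditional. On the protocol's own figures the expected catch is about 70 at a 30% reduction, 80 at 20% and 90 at 10%, against a target of at least 100. The 3% to 9% chance of reaching 100 assumes the 30% reduction, independent houses and a BBnet SD between 1.05 and 1.5.

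The antenatal malaria outcome is unaffected. The entomological description and the PermaNet 3 durability assessment are affected. This is a minor to moderate point.

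**What to change.** Keep 200 houses and one round, but sample both arms.

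- For example, take ten BBnet and ten PermaNet 3 areas with ten houses each (20 x 10 = 200), stratified so that all seven zones are covered. This also allows 30 durability houses per arm at no more than three per area.
- Report species composition and marker frequencies by arm and pooled, with no test of abundance.
- Replace the target of at least 100 with an expected catch of about 85. Give the bracket of about 70 to 100, which are the values if all houses caught at the BBnet or the PermaNet 3 rate, and say that the rates are borrowed. If 100 is truly needed, raise the number of houses instead.
- Reconcile the per-arm wording in section 3.3, and the per-arm sample and second survey round in section 4.3, with the single round and the arms actually sampled.

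The cost is about 20 areas to visit and liaise with instead of about ten, for the same number of houses. The rest is a change of text.

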4.2.3 Collection routine

Collections will take place in the morning (6-10am) and householders will be requested to keep doors and windows closed and to leave bednets in place as much as possible. Collections will use Prokopack aspirators and take approximately 20 min/house, providing a standardised methodology for collecting adult mosquitoes. Samples will be transferred to the University of Kinshasa School of Public Health for further processing, including morphological species identification, before transfer of *Anopheles* specimens to LSTM for molecular species identification and detection of *Plasmodium* infection, and molecular resistance diagnostic marker screening using quantitative PCR.

4.2.4 Molecular analyses of species and resistance

Following initial morphological identifications, species identity within morphologically indistinguishable species complexes will be performed using standard PCR diagnostic methods (*An. gambiae* and *An. funestus*) and additional specimens for which molecular identity is uncertain will be confirmed by mitochondrial DNA sequencing. Appropriate resistance diagnostic markers for each major species detected will be screened in the samples using quantitative PCR. Molecular analyses will be performed at LSTM. The frequency of a triple mutant linked with pyrethroid resistance (which is common throughout much of DRC) will be assessed. PBO is expected to block the action of this mechanism and determination of frequency of this mechanism. Voltage gated sodium channel (target site) mutations (at positions 402, 995, 1527, 1570) will also be assessed, and more novel mechanisms may also be assayed. Markers for Cyp6P9a,b and GSTe2 will be screened in *An. funestus*. Molecular analyses will be performed on female *Anopheles* adults collected as part of the routine surveys and also those from the double net and HLC collections (above). *Plasmodium* infection in each specimen will also be assessed. Molecular analyses will be performed using quantitative PCR.

4.3 Net durability

From N=30 houses per arm from the second survey round, one net will be chosen at random for removal and replacement with a new net of the same type for assessment of physical integrity, and chemical content using HPLC. The houses will a subset of those from which entomological collections are performed and no more than 3 houses should be chosen per health area to ensure even coverage. A standard durability monitoring protocol will record holes (and proportionate hole index). Sections of nets (30 x 30 cm) will be cut out to provide net sections for chemical (deltamethrin and PBO) content analysis using HPLC in Liverpool.

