Trial of PermaNet 3-barrier bednets as part of an operational distribution programme in Haut-Katanga province, DRC (BBnets)

Study protocol v2.2 29/02/24

amendments made to:

sections referring to multiple collection periods (there will only be one 3 month epidemiological data collection period and) one entomological collection period and the total data collection period will be up to 5 months rather than 7 months

bioavailability testing removed

Revised timeline added

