3.2 Household surveys

Following initial contact with community leaders facilitated by health centre staff, boundaries of the health areas will be mapped to delimit the area to be surveyed (and the GPS coordinates of each centre holding an ANC clinic will be recorded). Households within the health area will be visited by study personnel, accompanied by a local resident, typically a member of the community health worker's team. From a starting point, a first house will be chosen and subsequent houses sampled based on separation by approximately 50m. If householders are present, the purpose of the study and nature of the request for participation will be explained to them, and if they are willing to be enrolled the head of the household will be asked to sign a consent form, which will give permission (subject to verbal consent at the time of collection) to visit the house to conduct questionnaires of net use and perceptions. Prospective participants will be given up to 24 hours to decide whether to take part. If they do not wish to take part, or the head of the household), a neighbouring house will be approached. The questionnaire will be taken, and net hanging observed, including the position of barriers in houses with P3-BBnets. A photograph of bednets hanging *in situ*, excluding any people, may be taken subject to specific consent from the householder. An equal

number of P3-BBnet and PermaNet 3 houses will be surveyed. The information leaflet and consent form is provided in **Appendix B**. A total of approximately 200 houses will be sampled.

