5.2 Household survey data

Quantitative data from surveys will be compared among areas (for BBnet barrier suspension) and time points (for BBnet barrier suspension, net durability assessments, and ordinal questionnaire data) using ANOVA, t-tests or non-parametric equivalents as appropriate. For qualitative data, coding will use Atlas.ti v9.

6. Data recording, management and confidentiality

The clinic nursing staff and assistants are familiar with the procedures involved, which are routine, and training will be provided to the appointed member of clinic staff who will be a part of the wider study team and responsible for ensuring the protocol is followed and data recording occurs correctly. The study team will be in contact via telephone with the study-associated member of the clinic staff to emphasise key points and answer queries. The DRC project PI will be responsible for coding the data so that data analysis will be performed blind to the identity of clusters by another member of the study team (at LSTM). Data will be entered into an Access database as soon as possible after data collection. All data collected will be anonymous, and GPS locations of individual houses will not be used in any report or presentation. Any photographs taken will only be taken of bednets and will not show residents.

7. Ethical considerations

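### As written, the net durability rule yields no PermaNet 3 nets, names a survey round that is not planned, and leads to a time-point comparison that cannot be formed

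*Protocol*

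**What the plan says.** Protocol section 4.3 fixes the durability sample: "From N=30 houses per arm from the second survey round, one net will be chosen at random". Each net taken is replaced by a new one of the same type, then assessed for holes and for deltamethrin and PBO content. The houses must come from "those from which entomological collections are performed and no more than 3 houses should be chosen per health area".

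Section 3.3 describes the houses that supply this sample: "we aim to sample from approximately 10 health areas from the BBNet arm". It sets a target of 20 houses per health area and a total of about 200. Section 4.2.2 repeats the figure of 200 houses, again in BBnet-arm clusters, and provides for one survey round late in the trial. The lay summary also gives a single round of mosquito collections.

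Section 3.2 describes a separate household questionnaire survey of about 200 houses, in which an equal "number of P3-BBnet and PermaNet 3 houses will be surveyed".

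Section 5.2 assigns durability to comparisons across "time points (for BBnet barrier suspension, net durability assessments, and ordinal questionnaire data) using ANOVA, t-tests" or non-parametric equivalents. Comparison among areas is reserved for barrier suspension. No comparison of arms is listed for durability.

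**The concern.** Three statements about one small component do not fit together. The sample is specified per arm, but the houses it must come from lie in one arm only. It is tied to a second round, but only one round is planned. The analysis contrasts time points, but one round gives one time point.

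At stake is the ability to compare the wear and chemical content of the two net types after field use. The protocol describes the P3-BBnet as identical to a PermaNet 3 apart from the barrier, and the per-arm sampling with like-for-like replacement implies an intention to compare them. Nets that are not collected during the survey cannot be obtained at that age later, and an analysis plan cannot make up for nets that were never sampled.

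**Working it through.** **Inputs, all from current protocol text**

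- Durability target: 30 houses per arm, one net each (4.3).
- Cap: at most 3 durability houses per health area (4.3).
- Source: a subset of the mosquito-collection houses (4.3).
- Mosquito-collection areas: about 10, in the BBnet arm (3.3; arm repeated in 4.2.2).
- Houses per area: 20 (3.3). Total: about 200 (3.3 and 4.2.2).
- Rounds: 1 (lay summary and 4.2.2).

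**Step 1. Reproduce the stated total of 200.** Section 3.3 still expresses the 20 houses as a figure per area, per arm and per round, so it is worth checking which reading gives the total. Houses = areas × houses per area × arms × rounds.

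- One arm, one round: 10 × 20 × 1 × 1 = 200. This matches.
- Two arms, one round: 10 × 20 × 2 × 1 = 400. This does not match.
- Two arms, two rounds: 10 × 20 × 2 × 2 = 800. This does not match.

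Only a single arm and a single round give the stated total, in line with the explicit restriction to BBnet clusters. The per-arm and per-round wording in 3.3 therefore does not bring PermaNet 3 houses into the sample.

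**Step 2. Durability houses obtainable.** Maximum per arm = mosquito-collection areas in that arm × 3.

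- BBnet arm: 10 × 3 = 30 of 30. There is no slack; with 9 areas the maximum would be 9 × 3 = 27.
- PermaNet 3 arm: 0 × 3 = 0 of 30.

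**Step 3. Areas needed.** Under the cap, 30 houses in an arm require at least 30 / 3 = 10 health areas in that arm. The trial has 21 BBnet and 42 PermaNet 3 areas, so the requirement can be met in both arms, but not from the mosquito-collection houses.

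**Step 4. Round and contrast.** Section 4.3 asks for the second round and the plan provides one, so read literally the durability sample is never triggered. If the single round is used instead, durability is measured once and the time-point comparison in 5.2 has nothing to compare. The comparison that per-arm sampling could support, P3-BBnet against PermaNet 3, is not listed.

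The list of amendments at the front agrees that there is to be "one entomological collection period", but none of the steps depends on it.

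**The case against.** The strongest reply is that this is leftover wording in an ancillary assessment. Section 4.3 states no hypothesis, no powered contrast and no test. It asks plainly for 30 houses per arm, and the team will be visiting PermaNet 3 houses for the questionnaire survey anyway. A sensible field team would take nets there. That stands as a limit on severity. It does not remove the defect, because the team would have to depart from both the source of houses and the round that the protocol specifies.

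A reader might infer more than the documents support, in four ways.

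- **That the malaria result would become uninterpretable.** The protocol gives durability no formal role in explaining the primary result.
- **That the t-tests and ANOVA in 5.2 carry a quantifiable inflation of type I error from clustering.** The usual design-effect calculation applies to a comparison of arms, which 5.2 does not list. The protocol also gives no intraclass correlation for these outcomes and no number of houses per area for the questionnaire survey. No such figure is claimed here.
- **That the questionnaire data also have only one time point.** The single-round statements concern mosquito collection and ANC monitoring. Section 3.2 gives no number of household rounds and 4.4 still speaks of rounds in the plural. One round is plausible there but inferred.
- **That questionnaire items should be compared between arms.** The clearly ordinal items in Appendix F, such as how often the barrier is suspended, concern the barrier and have no PermaNet 3 counterpart.

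**Conclusion.** The point holds as an internal contradiction that makes the durability component unworkable as written: 30 of 30 BBnet houses with no margin, 0 of 30 PermaNet 3 houses, a round that is not planned, and a time-point contrast that one round cannot provide. The counts assume that the approximate figure of 10 areas is met exactly and that the cap of 3 is applied. The zero for PermaNet 3 depends on neither, only on the restriction of mosquito collection to BBnet clusters.

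That a between-arm comparison is wanted is implied by the per-arm sampling, not stated. The consequence is confined to a secondary assessment. The ANC1 prevalence endpoint and its 21 and 42 clusters are unaffected. The passages should be reconciled before nets are collected, but the trial's main conclusion is not at risk.

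**What to change.** **Section 4.3.** Draw the 30 nets per arm, in the single survey round, from the houses of the questionnaire survey in 3.2. As a minimum, draw the PermaNet 3 nets from those houses. Keep the cap of 3 per health area and state that at least 10 health areas per arm will be visited; 3.2 does not say how many it covers. Taking both arms from the same survey is preferable, since the two sets of nets are then selected in the same way.

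**Section 5.2.** For net durability, replace the time-point contrast with a comparison of arms that accounts for health area. Area-level summaries compared between arms would do, as would a mixed model with a small-sample correction, given that there may be only about 10 areas per arm. Keep barrier-specific questionnaire items descriptive within the BBnet arm.

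**Sections 3.3 and 4.4.** Remove the residual per-arm and multiple-round wording, or confirm what it refers to.

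**Cost.** The number of nets is unchanged, and houses in both arms are already visited. It is more than an edit of wording, however. Consent under 3.2 covers the questionnaire, whereas net removal has its own form (Appendix C), so that consent and the replacement nets must be taken to the questionnaire-survey houses. If that survey was planned in fewer than 10 areas in either arm, it would have to be spread over more.
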